10.1.2. Primary Efficacy Analysis

The primary efficacy endpoint (abstinence) is described in Section 4.1.1. Two primary objectives are described in Section 3.1. Two between-arm comparisons are planned, corresponding to the two objectives:

- Abstinence from Week 3 to Week 6: Arm B (cytisinicline 6 weeks) vs Arm A (placebo)
- Abstinence from Week 9 to Week 12: Arm C (cytisinicline 12 weeks) vs Arm A (placebo)

The abstinence endpoint is binary (success, failure). For each of the comparisons listed above, the two treatment arms will be compared in terms of the proportion of subjects classified as a success. All randomized subjects will be included in the comparisons according to their randomized arm (ITT analysis).

The statistical significance of each comparisons will be based on the odds ratio using exact computations for stratified 2x2 frequency tables and using Monte Carlo estimation if necessary. The stratifier will be clinical site, with the possibility of pooling clinical sites having a small contribution, as described below. If cytisinicline is not favored by the effect size point estimate, then the comparison will be designated as not statistically significant.

The estimated common odds ratio and its exact confidence interval (CI) will be reported. Also, the estimated odds ratio and exact (midp) confidence interval for the marginal 2x2 table across sites (unadjusted odds ratio), and the estimated difference in proportions and the associated derived exact confidence interval using the exact confidence interval on the odds ratio will be reported. The exact difference in proportion confidence interval will be derived using the method of Thomas (1971 and 1977).^{2,3}

Following is template SAS code for performing each of the statistical comparisons using SAS PROC FREQ:

```
proc freq data=data;
  exact fisher or comor egor;
  table s*x*y / nopercent nocol;
run;
```

Where

s: site designator (with the possibility of pooling)

x: Two-level arm designator with x=0 for control arm and x=1 for experimental arm.

y: Indicator of success(y=1) or nonsuccess (y=0).

The coding of x and y assures that an estimated odd ratio >1 indicates favorable outcome for experimental arm.

The output from SAS PROC FREQ for the above template will have three tables of interest for assessing success of the comparison, with the following steps to be used to extract relevant items and assess whether the statistical criterion has been met:

1. Table “Tests for Homogeneity of the Odds Ratios”: The P value preferred for the test of homogeneity is “Exact Pr <=P” (Zelen exact test). If the Zelen exact test is not computable (it is known to be susceptible to memory exhaustion), then use the Breslow-Day P value indicated as “Pr > Chisq”.
2. Table “Common Odds Ratio”: Extract from this table the “Mantel-Haenszel Estimate” of the odds ratio and the “Exact Conf Limits” of this odds ratio estimate.
3. Table “Exact Test of H0: Common Odds Ratio=1”: Extract “One-Sided Pr>=S” as the one-sided P value for the between-arm comparison. If this one-sided P value is less than or equal to the applicable one-sided favorable direction significance level specified above then statistical criterion for the between-arm comparison will have been met, and not met otherwise. Report whether significance has been met and the two-sided P value “Sum<=Point.” The two-sided P value is to be reported because it is conventional (and less confusing). Reporting the one-sided P value is optional but not recommended; if reported it requires an explicit labeling as one-sided.

If the number of subjects within a stratum (clinical site) is small, then clinical sites stratification may require pooling to create a pseudo-site. The criterion for pooling will be to pool clinical sites with fewer than 2 subjects in any treatment arm. The pseudo site will represent the effect of sites with relatively small contribution. For purposes of statistical analysis, a unique site identification number will be assigned to the pseudo-site; the original clinical site identification number will be used for the remaining sites (ie, sites that did not meet the criterion for pooling). If no clinical sites meet the criterion for pooling, the original clinical site identification number will be used in the statistical analysis.

10.1.2.1. Sensitivity Analyses

The sensitivity analyses described in this section will be performed separately for each of the primary efficacy endpoints (abstinence from Week 3 to Week 6, abstinence from Week 9 to Week 12). Sensitivity analyses for each endpoint will include the treatment arms of interest for that endpoint. That is, the sensitivity analyses for the abstinence from Week 3 to Week 6 endpoint will include the cytisinicline 6 weeks (Arm B) and placebo (Arm A) treatment arms and the analyses for the abstinence from Week 9 to Week 12 endpoint will include the cytisinicline 12 weeks (Arm C) and placebo (Arm A) treatment arms.

When there is evidence of material non-homogeneity of odds ratio across clinical sites then the interpretation of the results will be evaluated for each clinical site. The results of each clinical site can be assessed using Fisher’s exact test for the 2x2 table specific to that site, including the site specific odds ratio estimate and its confidence interval. The above code template for Fisher’s exact test and odds ratio confidence interval is modified as follows: delete “comor eqor” in the exact statement. This modification will produce a separate 2x2 table analysis for each site. Extract odds ratio confidence interval for each table from the “Confidence Limits for the Odds Ratio” table. Note: The assessment of the degree of variability of the site-specific odds ratio

estimates is also specified as a planned sensitivity analysis and is somewhat informative even if the interaction is not material.

The analyses described below as Effect Modification Analyses and Tipping Point Analyses will be conducted by an independent statistician ([name]; TriArc Consulting) who will document the results of these analyses in a statistical report that will be included as an appendix to the clinical study report.

Effect Modification Analyses (EMA)

The goal of the EMA will be to evaluate the degree to which arm effects estimated for discrete values of a baseline attribute differ. For example, an EMA of sex estimates sex-specific arm effects and evaluates whether these estimates differ. If a baseline attribute to be evaluated using EMA is not discrete, the attribute is made discrete by specifying cutpoints based on external criteria or using percentiles computed from the pooled data (median, tertiles, or quartiles), for example, baseline CO split at below 10 or not, or using pooled quartile values.

For each of the primary efficacy endpoints, the relationship between treatment arm and the proportion of subjects with abstinence will be evaluated within stratum defined by the effect modifier. Evidence of effect modification will be indicated by a material interaction between the baseline attribute and arm, with the criterion for a material interaction set at ≤ 0.10 . The interaction P value is a measure of the contribution to the statistical model of the interaction, and will be reported. For each stratum, the number (%) of subjects within each stratum with abstinence will be reported for each treatment arm. Odds ratios and their 95% CIs will also be reported. Forest plots will be used to display the stratum-specific 95% CIs.

Tipping Point Analyses

A tipping point analysis⁴ will be performed for each of the primary efficacy endpoints, including sensitivity analyses if applicable.

The goal of each tipping point analysis will be to assess the degree to which the assignment of cases defined as failure due to inability to assess for success would influence results. The tipping point evaluation will re-analyze the data for all possible reversals of the failure assignment to a success, and present the results in a graph.

10.1.3. Secondary Efficacy Analysis

The three secondary efficacy objectives are stated in Section 3.2. The secondary efficacy endpoints (continuous abstinence, risk of relapse [relapse free]) are described in Section 4.1.2.

The analysis for secondary objectives 1 and 2 will be done only if the corresponding primary comparison passes statistical criterion.

Two between-arm comparisons are planned for secondary objectives 1 and 2:

- Continuous abstinence from Week 6 to Week 24: Arm B (cytisinicline 6 weeks) vs Arm A (placebo)
- Continuous abstinence from Week 12 to Week 24: Arm C (cytisinicline 12 weeks) vs Arm A (placebo)

Each continuous abstinence endpoint is binary (success, failure). Note: For the secondary analyses, smoking abstinence during the follow up period only (Week 16 to Week 24) followed the Russell Standard of allowing up to 5 cigarettes and still be regarded as abstinent/success. Each analysis will then compare the treatment arms in terms of the proportion of subjects classified as a success using the same statistical methods as described above for the primary endpoint.

The analysis for secondary objective 3 will be conditional and performed only if both primary comparisons 1 and 2 pass statistical criterion. One between-arm comparison is planned for secondary objective 3.

- Reduction in Relapse from Week 6 to Week 24: Arm C (cytisinicline 12 weeks) vs Arm B (cytisinicline 6 weeks)

This endpoint is binary (relapsed, without relapse). The treatment arms will be compared in terms of the proportion of subjects without relapse (relapse-free) using the same statistical methods as described above for the primary endpoint.

10.2. Analyses of Other Efficacy Endpoints

The other efficacy objectives are stated in Section 3.3. The other efficacy endpoints are defined in Section 4.1.3. Analyses of the other efficacy endpoints will be exploratory. There will be no multiplicity protection scheme for these analyses, and the results of these analyses will be labeled as exploratory.

The results for each endpoint will be displayed graphically by treatment arm. Side-by-side bar charts may be used to display categorical endpoints, Kaplan-Meier figures will be used for time-to-event endpoints. For binary endpoints, forest plots may be used to display 95% CIs for the odds ratio.

For each of the other efficacy endpoints identified below, 3 between arm comparisons will be performed, where appropriate:

- Arm B (cytisinicline 6 weeks) vs Arm A (placebo)
- Arm C (cytisinicline 12 weeks) vs Arm A (placebo)
- Arm C (cytisinicline 12 weeks) vs Arm B (cytisinicline 6 weeks) (this comparison will be two-sided)

The statistical analyses that will be performed for binary endpoints will follow the specification as described for the secondary objectives according to whether the comparison is one-or two-sided. For other than binary endpoints, the analysis methodologies are described below.

10.2.1. 7-day Point Prevalence Abstinence

The 7-day point prevalence abstinence endpoints are binary (success, failure) endpoints defined at each of the following visits: Weeks 2 to Week 12, Week 16, Week 20, and Week 24. The analyses of point prevalence abstinence endpoints will be conducted using all subjects in the All Randomized Set. The analysis methodology for binary endpoints was described in secondary objectives.

10.2.2. Serum Cotinine Levels

Serum cotinine levels will be measured every other week from Week 2 to Week 12, then at Week 16, Week 20, and Week 24.

Serum cotinine levels may be reported by the central laboratory as less than the lower limit of quantitation (eg, result reported as “<10 ng/mL”) or greater than the upper limit of quantitation (eg, result reported as “>2000 ng/mL”). Results reported as “<X” will be converted to a numeric result of “X – 1” prior to statistical analysis (eg, <10 ng/mL will be converted to 9 ng/mL). Results reported as “>X” will be converted to a numeric result of “X+1” prior to statistical analysis (eg, >2000 ng/mL will be converted to 2001 ng/mL).

Summary tables and figures of serum cotinine levels by treatment arm and visit will be provided for the All Randomized Set.

The treatment arms will be compared (cytisinicline 6 weeks vs placebo, cytisinicline 12 weeks vs placebo) using repeated-measures analysis of variance models with fixed effect term for treatment arm, visit and visit * treatment arm interaction. A compound symmetry covariance matrix will be used. The between-arm difference in means, their respective 95% CIs and Bonferroni-adjusted p-values will be reported. Forest plots may be used to display 95% CIs for the differences of the means.

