7. STUDY DESIGN OVERVIEW

7.1. Study Design

This will be a multi-center, double-blind, randomized, placebo-controlled, Phase 3 study conducted in male or female adults who are ≥ 18 years age, current daily cigarette smokers, intending to quit smoking, and are willing to set a quit date within 5-7 days of being randomized on the study. Study treatment must start the day after randomization such that study treatment is initiated prior to the quit date.

Subjects must meet all requirements outlined in the inclusion and exclusion criteria. Approximately 750 subjects will be randomly assigned with equal probability (1:1:1) to three arms: (Arm A, 12 weeks placebo: N=250; Arm B, 6 weeks cytisinicline followed by 6 weeks placebo: N=250; Arm C, 12 weeks of cytisinicline) as shown in the study design figure below.

Figure 2: ACH-CYT-04 (ORCA-3) Study Design Overview

This study will be conducted at approximately 15-19 clinical sites across the US. Subjects will be randomized within site, with the goal of balancing between arm allocation within clinical sites in order to minimize imbalance for the assessment of evidence of heterogeneity of effect estimates across sites. Clinical sites will be used as a stratification factor in primary analyses.

The study will be comprised of a pre-study screen, followed by 12 weeks of treatment, and post-treatment follow up visits to 24 weeks post-randomization.

Each randomized subject will receive 12 weeks of treatment using a TID dosing schedule. Determination of smoking cessation will be made from the subject's self-report of abstinence accompanied by expired carbon monoxide (CO) biochemical verification. Assessments of smoking abstinence will begin on Week 2 (Day 14±1 post-randomization) and will continue weekly during the Treatment Period, then at the Weeks 16, 20 and 24 Follow-up Period visits.

All subjects will receive concurrent smoking cessation behavioral support during the study Treatment Period (Weeks 1-12). Additional behavioral support will be provided during the Follow-up period based on issues/concerns/questions raised by the subject.

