9.6. Method of Assigning Subjects to Arms

Subjects will be allocated to arms according to a predetermined randomization schedule and randomly assigned with equal probability (1:1:1) once all screening procedures are completed and verified. Randomization will be stratified by site.

The clinical research staff will record study drug (tablet) administration and all related information on the applicable source documents, to allow investigational product accountability and evaluation of subject compliance.

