8.5. Baseline Smoking and Nicotine Testing

The following baseline data related to smoking will be summarized by treatment arm for both the All Randomized Set and the Safety Set:

- Average number of cigarettes smoked per day over 7 consecutive days, as reported in the subject diary
- Expired CO (ppm) at SV1
- Expired CO (ppm) at Day 0
- Cotinine result (ng/mL) at SV1.

If nicotine metabolism ratio (NMR) testing is done at SV1 then NMR will be derived as the ratio of the results for 3-hydroxycotinine (3-OH cotinine) and cotinine (ie, 3-OH cotinine / cotinine) and summarized by treatment arm.

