10.2.12. Number of Cigarettes Smoked Over Time

The number of cigarettes smoked will be collected every week from Week 2 to Week 12, then at Week 16, Week 20, and Week 24.

The treatment arms will be compared (cytisinicline 6 weeks vs placebo, cytisinicline 12 weeks vs placebo) using repeated-measures analysis of variance models with fixed effect terms for treatment arm, visit and visit * treatment arm interaction. The between-arm difference in means, their respective 95% CIs and Bonferroni-adjusted p-values will be reported. A figure for the number of cigarettes smoked by treatment arm and visit will be provided for the All Randomized Set.

An additional analyses will be performed by abstinence status for the primary endpoint (Weeks 3 – 6 and Weeks 9 -12).

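### The exploratory repeated-measures models leave out baseline and site, and the cigarette model uses counts whose reporting period changes from 7 to 9 days and is unstated in follow-up

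*SAP*

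**What the plan says.** SAP 10.2.2 (cotinine) and 10.2.3 (CO) specify "repeated-measures analysis of variance models with fixed effect term for treatment arm, visit and visit * treatment arm interaction", with compound symmetry as the covariance. SAP 10.2.12 (cigarettes) specifies "repeated-measures analysis of variance models with fixed effect terms for treatment arm, visit and visit * treatment arm interaction" and names no covariance. It adds: "A figure for the number of cigarettes smoked by treatment arm and visit will be provided for the All Randomized Set". None of the three sections lists baseline or site.

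Both are at hand. SAP 8.5 summarizes cotinine from the first screening visit, CO from the first screening visit and Day 0, and, for cigarettes, "Average number of cigarettes smoked per day over 7 consecutive days, as reported in the subject diary". Protocol 9.6 states: "Randomization will be stratified by site". The promise to use site in the analysis is limited. Protocol 7.1 says: "Clinical sites will be used as a stratification factor in primary analyses". Of the endpoints considered here, SAP 10.2 says that "the results of these analyses will be labeled as exploratory".

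For the cigarette count, Protocol 12.2.3 asks at each treatment visit from Week 2 for a total reaching back to the preceding visit. Those visits are 7 days apart up to Day 77 (Week 11); the Week 12 visit is on Day 86. Protocol 12.2.4 asks for a total at Weeks 16, 20 and 24 without naming a period. The two yes/no items just before it use different periods: since the preceding visit, and the past 7 days.

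**The concern.** There are two separate issues.

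- **Covariates.** When an outcome's own baseline is measured and randomization is stratified by site, adjusting for both is the usual cheap way to narrow the intervals of a randomized comparison. Leaving them out is not an error, but it gives up precision in three reported sets of arm differences.
- **Units.** SAP 10.2.12 puts counts over unequal periods into one model and one figure. A step at Week 12 would come from the calendar rather than from behavior, and it would fall at end of treatment, where readers look. Counts over longer periods also vary more, so a covariance with one common variance would misstate standard errors. The section does not say which covariance applies.

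**Working it through.** The documents give no standard deviation, baseline-outcome correlation, site variance share or precision target for these three outcomes, so there is no stated figure to reproduce. The one sizing figure (95.7% power) concerns binary abstinence and does not bear on this point.

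**1. Gain from baseline and site, single-visit arm difference**

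Fractional narrowing = 1 − sqrt((1 − r²)(1 − s)), where r is the overall correlation between baseline and outcome and s is the site share of variance. Both are assumed.

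| r (s = 0) | Narrowing |
|---|---|
| 0 | 0% |
| 0.1 | 1 − sqrt(0.99) = 0.5% |
| 0.2 | 1 − sqrt(0.96) = 2.0% |
| 0.3 | 1 − sqrt(0.91) = 4.6% |
| 0.4 | 1 − sqrt(0.84) = 8.3% |
| 0.5 | 1 − sqrt(0.75) = 13.4% |

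Site alone, at s = 0.05: 1 − sqrt(0.95) = 2.5%. A small simulation (six replicates per setting, compound symmetry, 500 subjects, 9 visits, 19 sites, s about 0.01) gave about 1.7% at r = 0.2 and 12.7% at r = 0.5.

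Why r may be modest: abstainers near zero dilute the correlation. The ORCA-1 Week 4 rates are 10% on placebo and 50% on 3 mg TID (Protocol 4.3). Take r = ρ·CV·mean(1 − p) / sqrt(mean[(1 − p)(CV² + p)]), with means over the two arms and abstainers at zero.

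- CV 0.4, within-smoker ρ 0.4: 0.112 / sqrt(0.282) = 0.21, narrowing 2.2%.
- CV 0.6, ρ 0.7: 0.294 / sqrt(0.422) = 0.45, narrowing 10.8%.

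CV and ρ are again assumed.

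The SAP does not say whether differences are per visit or averaged. For an average over 9 visits with assumed between-visit correlation 0.6, replace r² by r²/f, where f = (1 + 8 × 0.6)/9 = 0.644. The gain is then 3.2% at r = 0.2 and 21.8% at r = 0.5.

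Cost if the covariates carried no information: 19 extra terms in 500 subjects widen intervals by about sqrt(498/479) − 1 = 2.0% if balance were left to chance. Site-stratified blocks reduce the site part of that.

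**2. Cigarette count at a constant 10 per day** (the entry minimum, Protocol 8.1)

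| Visit | Nominal days | Plotted value |
|---|---|---|
| Weeks 2-11 | 7 | 70 |
| Week 12 | 86 − 77 = 9 | 90 |
| Week 16, whole interval | 112 − 86 = 26 | 260 |
| Weeks 20, 24, whole interval | 28 | 280 |
| Weeks 16-24, past 7 days | 7 | 70 |

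The days are nominal. With the visit windows, a weekly count can span 5 to 9 days and the Week 12 count 7 to 11. The Week 11 instructions in Protocol 12.2.3 also remind subjects of a Day 84 appointment for Week 12, while the visit itself is set for Day 86; the two should be reconciled.

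**3. Standard errors if one common variance were fitted to the counts**

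Ratio = sqrt(mean variance / own variance) over the 14 visits, complete data.

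- Whole-interval, SD proportional to days: mean variance (10 + 1.65 + 13.80 + 32)/14 = 4.10 times the weekly variance. Ratios are 2.03 at Weeks 2-11 and 0.51 at Weeks 20-24.
- Whole-interval, variance proportional to days: mean 23/14 = 1.64. Ratios are 1.28 and 0.64.
- Past 7 days: only Week 12 moves much, to 0.80 or 0.89.

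**4. Bias**

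All arms share the same schedule, and the arm-by-visit term is in the model. At any one visit the nominal period is the same in each arm, so the visit-specific arm difference is unbiased. Only comparisons or averages across visits mix units.

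**The case against.** The covariate half can fairly be called a preference. An unadjusted randomized comparison is valid, the analyses are exploratory, and SAP 10.3 foresees models with several explanatory variables. A reader might infer that omitting site breaks a commitment; it does not, because the promise covers the primary analyses only. What remains is that models added under 10.3 would carry the data-directed label and so would not be prespecified.

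The percentages are not document figures. That stands in full: they scale with an assumed correlation and vanish without it.

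It can also be said that raw counts are inferred, since a derived variable might sit in the ADaM specifications, which are not shown. But 10.2.12 opens with the number collected at each visit and gives no conversion to a rate, so the shift at Week 12 follows from the text as written.

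A reader might infer that the figure will show a fourfold rise after treatment. The documents do not establish this. The allowance of five cigarettes in total over follow-up (SAP 4.1.2.1) and the dating of the sixth (SAP 4.1.3) point to whole-interval counts, but the neighboring past-7-day item leaves it open. The eCRF and Data Entry Guidelines would settle it. The standard-error ratios further need a common variance, which 10.2.12 does not specify.

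Lastly, adding a baseline covariate could drop subjects whose baseline is missing. That is a fair objection, and the fix has to deal with it.

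**Conclusion.** The point holds at low severity. The three models omit an available baseline and the randomization stratifier. The loss is precision alone: about 0.5% to 13% of interval width at a single visit for an assumed overall correlation of 0.1 to 0.5, plus 0% to 2.5% for an assumed site share of 0% to 5%. No bias results and no primary or secondary conclusion changes.

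The cigarette analysis is under-specified in a way that needs no assumed parameter: no unit, period or covariance is stated, and the nominal period lengthens from 7 to 9 days at Week 12. The size of any follow-up distortion depends on a field definition that is not in the documents. It would be wrong to read this as biased arm differences at individual visits.

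**What to change.** 1. In SAP 10.2.2, 10.2.3 and 10.2.12, add the subject's own baseline (as defined in SAP 6.3; diary cigarettes per day for 10.2.12), baseline-by-visit, and site pooled by the existing rule in SAP 10.1.2: "The criterion for pooling will be to pool clinical sites with fewer than 2 subjects in any treatment arm". State a simple rule for missing baselines, for example mean imputation of the covariate, so that no randomized subject is dropped for want of one.
2. In 10.2.12, confirm the period of the follow-up count from the eCRF and state it. Then analyze and plot cigarettes per day: the count divided by the actual days in its period (days since the last attended visit, or 7 if it is a past-7-day count).
3. Name for 10.2.12 a covariance that lets variances differ by visit and does not assume equal spacing, such as heterogeneous compound symmetry. Visits are weekly to Week 12 and four-weekly afterwards, so a structure tied to visit order would fit poorly.
4. State whether the reported differences are by visit, averaged, or both.

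The cost is SAP and program edits before unblinding and one check of the eCRF count field. No new data are needed, and the primary and secondary analyses are untouched.

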2.2. Determination of Sample Size

In the 2011 published TASC Phase 3 study that evaluated cytisine versus placebo for 25 days in 740 primarily moderate-to-heavy smokers in Poland, the sustained 6-month abstinence rate was 10.0% in the cytisine arm compared to 3.5% in the placebo arm ($P<0.001$). In the 2014 published Phase 3 study that evaluated cytisine for 25 days versus nicotine replacement therapy (NRT) for 8 weeks in 1,310 adult daily smokers in New Zealand, the continuous six-month abstinence rate was 22% in the cytisine arm compared to 15% in the NRT arm ($P=0.002$).

Data from the international EAGLES trial ($N=8,120$) were used to assess predictors for continuous smoking abstinence outcomes from Weeks 9-24. These analyses provided evidence that subjects treated in the US had lower success rates of quitting, regardless of treatment (varenicline, bupropion, or NRT). The continuous abstinence rates from 9-24 weeks in the US were 16.1%, 11.4% and 10.6% for varenicline, bupropion, or NRT, respectively, compared to 6.7% for placebo treatment. The odds ratios (OR) for these treatments in the US were 2.66, 1.78, and 1.64, respectively. The lower success rate in US smokers supports the view that smokers in the US may have particular characteristics that make it more difficult for them to stop smoking.

The trial size for this study is specified as 250 subjects per arm. The assumed control arm probability of success (continued abstinence to Week 24) is 0.07 (7%). The hypothesized experimental arm minus control arm probability difference is specified as 0.12 (12 points), corresponding to a hypothesized odds ratio of 3.116 (eg, 7% for placebo vs 19% for cytisinicline treatment). The significance level to be used is adjusted from the overall type I error probability of one-sided 0.025 to one-sided 0.0125 using the Bonferroni method to control for multiplicity. The statistical operating characteristics for each comparison are illustrated using simulation of Fisher's exact test with 10,000 replicates. These specifications are consistent with 95.7% power for each comparison with, conditional on 0.07 control arm probability outcome, an odds ratio critical region of ≥ 1.83 , corresponding to a critical difference of ≥ 0.051 (7% for placebo vs 12% for cytisinicline treatment). The trial sizing simulations were not done using the Hochberg method for controlling inferential multiplicity for the two primary comparisons. (The use of the

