10.2.3. Expired CO Levels

Expired CO levels (ppm) will be measured every week from Week 2 to Week 12, then at Week 16, Week 20, and Week 24.

Summary tables and figures of expired CO levels by treatment arm and visit will be provided for the All Randomized Set.

The treatment arms will be compared (cytisinicline 6 weeks vs placebo, cytisinicline 12 weeks vs placebo) using repeated-measures analysis of variance models with fixed effect term for treatment arm, visit and visit * treatment arm interaction. A compound symmetry covariance matrix will be used. The between-arm difference in means, their respective 95% CIs and Bonferroni-adjusted p-values will be reported. Forest plots may be used to display 95% CIs for the differences of the means.

An additional analyses will be performed by abstinence status for the primary endpoint (Weeks 3 – 6 and Weeks 9 -12).

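### The cotinine and expired-CO models fix compound symmetry with no fallback, so per-visit 95% intervals are miscalibrated if the variance differs between visits

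*SAP*

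**What the plan says.** SAP 10.2.2 (cotinine) and 10.2.3 (expired CO) use the same repeated-measures model, with "fixed effect term for treatment arm, visit and visit * treatment arm interaction". Each fixes the covariance in one sentence: "A compound symmetry covariance matrix will be used". Neither gives an alternative structure, a robust standard error, a degrees-of-freedom method or a check of the assumption.

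The visit schedules are:
- Cotinine: "Serum cotinine levels will be measured every other week from Week 2 to Week 12, then at Week 16, Week 20, and Week 24". That is 9 visits.
- CO: "Expired CO levels (ppm) will be measured every week from Week 2 to Week 12, then at Week 16, Week 20, and Week 24". That is 14 visits.

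The promised output is: "The between-arm difference in means, their respective 95% CIs and Bonferroni-adjusted p-values will be reported". The text does not say whether these differences are per visit or averaged over visits. Objectives 2 and 3 in SAP 3.3 name the visits, and the interaction term makes per-visit contrasts available, so a per-visit reading is natural but inferred.

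On status, SAP 10.2 says: "Analyses of the other efficacy endpoints will be exploratory". SAP 10.2.12 uses the same type of model for cigarettes smoked and names no covariance structure.

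**The concern.** Compound symmetry assumes the same variance at every visit and the same correlation for any two visits, whether 2 or 22 weeks apart. With arm, visit and interaction terms and complete data, the model then gives every visit the same standard error, built from the average variance. If cotinine or CO is more variable at some visits than at others, the reported interval is wrong at both kinds of visit.

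There is some reason to doubt equal variances. Active drug stops at Week 6 in Arm B and at Week 12 in Arm C, and each visit mixes abstinent subjects with continuing smokers. At stake are the per-visit intervals and p-values, and any forest plots drawn from them, for these exploratory measures.

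**Working it through.** **Inputs from the documents.** The 9 and 14 visits and the model are those given above. On size, SAP 2.2 says: "The trial size for this study is specified as 250 subjects per arm". The plan states no figure for these models. Its sizing figure (95.7% power) concerns the primary binary comparisons and does not depend on this point; exact enumeration of Fisher's test reproduces it at 95.75%.

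**Assumptions.** No SD or correlation by visit is given. I let the SD change linearly in time from Week 2 to Week 24 by a factor of 1.25 to 2, in either direction, and also tried constant and non-monotone patterns.

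**Formula.** With complete data, the compound-symmetry interval at visit j, relative to the correct one, has width ratio r_j = sqrt(mean variance over visits) / SD_j. Its coverage is 2Φ(1.96 r_j) − 1.

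**Worked case: cotinine, SD rising from 1 to 1.5.**
- SDs at Weeks 2, 4, 6, 8, 10, 12, 16, 20 and 24: 1, 1.045, 1.091, 1.136, 1.182, 1.227, 1.318, 1.409, 1.5.
- Mean variance = 13.450/9 = 1.494; square root 1.2225.
- Week 2: r = 1.2225/1 = 1.22; coverage 98.3%.
- Week 24: r = 1.2225/1.5 = 0.815; coverage 89.0%.

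**Cotinine, range of assumptions (coverage at Week 2 / Week 24).**

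| SD change | Rising | Falling |
|---|---|---|
| 1.25-fold | 97.0% / 91.8% | 92.8% / 97.5% |
| 1.5-fold | 98.3% / 89.0% | 91.0% / 98.9% |
| 2-fold | 99.6% / 84.7% | 88.5% / 99.8% |

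For CO with 14 visits, a 1.5-fold change gives 98.0% / 87.9% rising and 91.8% / 99.1% falling. For cotinine, a U-shaped SD (1.5 to 1 to 1.5) gives 91% at both ends, and a hump-shaped SD gives 98% at both ends. A constant SD gives 95% at every visit.

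**Simulation check.** REML compound-symmetry fit, 9 visits, 250 per arm, 400 replicates (Monte Carlo SE about sqrt(0.95 × 0.05/400) = 1.1 points). The true correlation was either exchangeable at 0.6 or 0.97 to the power of the weeks apart. Dropout by Week 24 was 0% or 25%, at random.
- SD rising 1.5-fold, exchangeable, no dropout: 98.5% at Week 2, 90.2% at Week 24.
- SD falling 1.5-fold, exchangeable, no dropout: 91.5% and 98.5%.
- Constant SD, decaying correlation, no dropout: 95.8% to 98.0%, so no shortfall.
- Constant SD, decaying correlation, 25% dropout: 92.5% at Week 24.
- SD rising 1.5-fold, decaying correlation, 25% dropout: 85.8% at Week 24.
- Difference averaged over visits, all scenarios: 92% to 97.5%.

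**After the change.** With a separate variance at each visit, r_j = 1 and complete-data coverage is 95% throughout. A further simulation took the correlation as 0.35 + 0.60 exp(−weeks/10), with about 25% dropout depending on the last value. With the SD rising 1.5-fold, compound symmetry covered 99% at Week 2 and 88% at Week 24. Across its constant and rising-SD scenarios, an unstructured matrix covered 93% to 96.5%.

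**The case against.** The strongest reply is that nothing in the documents shows unequal variances, and that changing quit rates alone would hardly produce them.

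Take abstinent subjects at zero, a share q of them in each arm, and a smoker coefficient of variation c (assumed 0.4 to 0.8). The within-arm variance is then proportional to (1 − q)c² + q(1 − q). Let q fall from 50% (ORCA-1, 3 mg TID arm, end of treatment; Protocol 4.3) to 19% on active drug, and from 10% to 7% on placebo (late values from SAP 2.2). Summing the two arms:
- c = 0.4: sqrt(0.497/0.564) = 0.94.
- c = 0.8: sqrt(1.333/1.236) = 1.04.

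That is nearly flat. A larger change needs continuing smokers' own levels to shift. If their on-treatment level were 80% of their Week 24 level, the ratio would be 0.94/0.8 = 1.17 to 1.04/0.8 = 1.30. The documents neither support nor exclude this.

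This reply stands as a limit on size and direction. It does not defend fixing a structure that fails if the assumption is wrong.

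Three further replies also stand. The analyses are exploratory. By-visit summaries are planned, and the default statistics in SAP 6.2 include the SD, so a change in variance would be visible. And if only a visit-averaged difference is reported, the effect is small.

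**Conclusion.** The point holds as a cheap improvement. Compound symmetry is fixed for both models with no fallback, and per-visit intervals are miscalibrated to the extent that the variance differs by visit. At the high-variance end, cotinine coverage is about 92% to 85% (SD rising) or 93% to 88.5% (SD falling) for a 1.25- to 2-fold change. Those factors are assumptions, and per-visit reporting is inferred rather than stated. No primary or secondary conclusion is affected.

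A reader might infer three stronger things that the documents do not support:
- **Intervals too wide early and too narrow late.** This holds only if the variance rises. It reverses if the variance falls, and both ends err the same way under a U or a hump.
- **Weeks 16 to 24 will look more certain than they are.** This needs the same unsupported direction, or else decaying correlation with dropout, where the loss at constant variance is only to about 92.5% at Week 24.
- **Unequal visit spacing is the cause.** With constant variance and complete data there is no shortfall. Spacing bears on the correlation assumption, which matters mainly when visits are missing.

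**What to change.** In SAP 10.2.2 and 10.2.3, replace the covariance sentence with an unstructured matrix across visits and Kenward-Roger degrees of freedom. State the order to follow if it does not converge:
1. Heterogeneous Toeplitz. This frees the visit variances, though its correlations follow visit order rather than elapsed weeks.
2. Compound symmetry with empirical (sandwich) standard errors. This comes last because it repairs the standard errors but not the assumed correlation, on which the estimates rely when visits are missing.

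State the same structure in SAP 10.2.12.

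The cost is one line per section. The downside is more covariance parameters: 9 × 10/2 = 45 for cotinine and 14 × 15/2 = 105 for CO, against 2 now. With about 750 subjects this is feasible, and the fallback covers non-convergence. Fixing the order in advance also avoids choosing a structure after unblinding.
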